#### **1.2 Health literacy and health inequalities**

There is a link between socioeconomic deprivation and low Health Literacy. That is, those with lower Health Literacy are more likely to be from socially deprived areas and have no educational qualifications (Roberts, 2015).

Low Health Literacy is associated with:

- Unhealthy lifestyles and poorer general health
- Low use of preventative services e.g. vaccinations and screening
- Increased attendance at A&E and hospital admissions
- Decreased life expectancy

(NHS 2023. NIHR, 2022, Roberts, 2015).

If Health Literacy is improved this can positively affect treatment adherence, and lead to reduced numbers of call backs, cancelled appointments and improved satisfaction and outcomes (Roberts, 2015). It has been suggested that interventions to improve Health Literacy will best be targeted at those with lower levels of

education, those living in the most deprived areas, and those with a limiting health condition or disability (Roberts, 2015).

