#### 1.3.7 The proposed Theory of Change

For the Live Life Better Derbyshire service, the training will help staff to communicate in simpler language and check service users' understanding of actions they need to take. This will help service users to understand what they need to do to lose weight, be activated to self-manage their weight, take actions to lose weight, and adhere to the 12 week programme. This will help them to lose weight and maintain weight loss.

For the Pulmonary Rehabilitation service, the training will help staff communicate in simpler language and check service users' understanding of the actions they need to undertake. This is so service users will understand what they need to do to improve their exercise tolerance and respiratory health, be more likely to take actions, and thus improve their overall health. It is hoped the intervention will also help activate people to continue to manage their own physical and respiratory health beyond the programme and know what to do should they suffer an acute exacerbation.

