## **2. Research question and aims & objectives**

### **2.1. Research question**

Can a Verbal Health Literacy training intervention for health workers improve health outcomes and reduce health inequalities for people using their services?

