### **2.2. Aim**

To investigate whether a Verbal Health Literacy training session for staff, with accompanying tailored support from a Health Literacy Officer to help implement the techniques into practice, can improve health outcomes for patients.

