### **2.3. Objectives**

- a) To understand staff perceptions of the acceptability and feasibility of the Verbal Health Literacy training session, and the support to use the techniques in practice from the Health Literacy Officer.
- b) To understand staff knowledge of the Verbal Health Literacy techniques and their confidence and skills to use them.
- c) To understand how the Verbal Health Literacy techniques taught in the training session are being actioned in practice.
- d) To determine whether subjective Health Literacy and activation skills, such as the ability to self-manage, engage with healthcare services and understand what actions to take, are improved for service users after attending programmes delivered by Verbal Health Literacy trained members of staff.
- e) To measure the impact of the Verbal Health Literacy training on health and wellbeing outcomes.
- f) To describe the Index of Multiple Deprivation quintile of attendees at programmes and compare with the Derbyshire population in order to assess impact on health inequalities.

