#### 3.10.5 Aggregate service data

For the aggregated outcome data we will compare mean change in an outcome in a three month period before the training and in the three month period after the training for trained and untrained groups. Means and standard deviations will be provided by the services, that is, no individual data will be shared with researchers.

To meet the final objective, we will compare the IMD quintiles for attendees at the programmes in the three month period post-training with the IMD quintiles for the IRAS 336469

Derbyshire population. The expectation is that the % of people in socially deprived quintiles will be higher for the programmes than for the Derbyshire population.

SPSS and Excel spreadsheets will be used to store, organise and assist in analysis of the quantitative data from multiple sources.

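### The deprivation comparison in objective (f) describes who attends; as planned it cannot assess the training's impact on health inequalities

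*Combined protocol and SAP*

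**What the plan says.** The research question (section 2.1) asks whether the training can "improve health outcomes and reduce health inequalities for people using their services". The Aim (section 2.2) is narrower: it asks whether the training "can improve health outcomes for patients" and does not mention inequalities.

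Objective (f) in section 2.3 opens as a description of attendees' Index of Multiple Deprivation (IMD) quintile. It then gives its purpose: to "compare with the Derbyshire population in order to assess impact on health inequalities".

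Section 3.10.5 states the analysis for this final objective: "we will compare the IMD quintiles for attendees at the programmes in the three month period post-training with the IMD quintiles for the" Derbyshire population. It adds: "The expectation is that the % of people in socially deprived quintiles will be higher for the programmes than for the Derbyshire population".

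The paragraph before it does plan a before-and-after contrast, "in the three month period after the training for trained and untrained groups", but only for mean change in an outcome.

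Section 3.7 requests aggregate IMD quintiles, attendance, non-attendance and completion for periods in 2023 and 2024, with the same data for weight programmes run by untrained staff. It says that data for the two periods will let change be measured at service level. Section 3.5 also provides individual IMD for consenting service users.

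**The concern.** The stated purpose is causal (impact), but the contrast assigned to it is descriptive (attendees against the general population after training). In the weight service only four of eight staff are trained (section 3.2), and the comparison as worded makes no split between their groups and the others.

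The plan already expects deprived quintiles to be over-represented. If they are, objective (f) as worded invites that result to be read as an effect on inequalities, when it may only show who already used the services. Section 8 says the findings are meant to inform commissioners' funding decisions, so the label matters.

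**Working it through.** **1. The sections side by side**

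| Element | Where | What it covers |
|---|---|---|
| Inequality question | 2.1 | Inequalities among people using the services |
| Purpose of (f) | 2.3 | Impact on inequalities |
| Analysis for (f) | 3.10.5 | Attendees after training against the county; no 2023 period, no trained/untrained split |
| Before/after, trained/untrained | 3.10.5 | Mean change in an outcome only |
| Regressions | 3.10.4 | Mean change; no IMD term named |
| IMD data requested | 3.7, 3.5 | 2023, 2024, untrained control; individual IMD for consenters |

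The data for a controlled comparison are requested, but no analysis applies them to (f). Nothing examines outcomes, completion or non-attendance by IMD.

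**2. Plan's own figures**

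The plan gives no figure for (f). Its one sample size (section 3.9.3) reproduces: 2 × (1.960 + 0.842)² × 1.6² / 0.4² = 251.2, rounded up to 252 per group. The SD of 1.6 kg and the 0.4 kg target are reused in step 6.

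**3. Can the expected result appear with no training effect?**

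The documents give no IMD shares, so these are assumptions: population share p₀ = 20% in the most deprived quintile, and attendee share q the same before and after training. Attendee numbers are from section 3.9.2: 660 for the weight service and 144 for pulmonary rehabilitation (its three-month maximum).

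Chance of a significant excess = Φ{[(q − p₀) − 1.96·√(p₀(1−p₀)/N)] / √(q(1−q)/N)}

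| Existing intake q | N = 660 | N = 144 |
|---|---|---|
| 20% | 2.5% | 2.5% |
| 25% | 88% | 34% |
| 30% | over 99.9% | 82% |

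Example, N = 660 and q = 25%: (0.05 − 0.0305) / 0.01686 = 1.16, and Φ(1.16) is about 0.88.

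**4. Does the comparison respond to training at all?**

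Yes. Take 330 trained-group and 330 untrained-group attendees (section 3.9.3), and suppose training raised the deprived share by 5 points in trained groups only. The planned result is [330(s + 0.05) + 330s]/660 − 0.20 for existing share s.

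| Existing share s | No effect | +5 points in trained groups |
|---|---|---|
| 20% | 0 | +2.5 |
| 25% | +5 | +7.5 |
| 30% | +10 | +12.5 |

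The result moves by 2.5 points, but it also contains an unknown intake component (0 to +10 over the shares chosen here), and nothing in the comparison separates the two. Equally, an observed share of 30% gives +10 points whether the earlier share was 20%, 25%, 30% or 35%, that is, a change of +10, +5, 0 or −5.

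**5. Precision of the controlled change in IMD share**

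Assume 330 per arm in each period (2023 size taken as equal) and no clustering. Half-width = 1.96·√(4·p(1−p)/330):
- p = 20%: 8.6 points
- p = 40%: 10.6 points
- p = 50%: 10.8 points

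**6. Precision of an optional training-by-IMD term in the weight regression**

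Take 160 consenters per arm (section 3.9.2), SD 1.6 kg, and an assumed deprived share p. Half-width = 1.96 × 1.6 × √{2[1/(160p) + 1/(160(1−p))]}:
- p = 50%: 3.136 × √0.0500 = 0.70 kg
- p = 20%: 3.136 × √0.0781 = 0.88 kg

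The plan's target difference is 0.4 kg. These widths scale directly with the SD.

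**The case against.** The strongest reply is that the gap is narrow. Objective (f) begins as a description, the expectation in section 3.10.5 is descriptive, and the Aim omits inequalities. Section 3.7 collects the 2023 and control-group data and says the two periods allow change to be measured, so a service-level comparison of IMD mix may well be intended. This stands in part. A reader might infer that the plan has no earlier or control data on deprivation; section 3.7 shows otherwise. What is missing is the link from those data to the final objective.

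A second reply is that reach plus average benefit is itself an inequality argument. Section 1.2 reports a suggestion that such interventions are best aimed at, among others, "those living in the most deprived areas, and those with a limiting health condition or disability". If deprived people are over-represented and training helps on average, the gain falls more on them. That is coherent, but the plan neither states it nor checks that deprived attendees benefit as much as others.

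Third, the illustration supposes an effect on attendee mix that the documents do not propose. The theory of change (section 1.3.7) works through understanding and activation: "This will help service users to understand what they need to do to lose weight, be activated to self-manage their weight". Entry is by referral or self-referral (section 3.8.2). This is fair: the figures show the logic and estimate nothing about this study. It also makes attendee mix an unlikely place to see an effect of staff training.

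**Conclusion.** The point holds. The one analysis assigned to (f) measures reach. It cannot separate a training effect from existing intake, and no other planned analysis fills the gap, so the inequality half of section 2.1 cannot be answered as written. The probabilities and point shifts rest on assumed IMD shares; the conclusion follows from the structure of the comparison and does not depend on them.

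Three stronger readings are not supported:
- That the population comparison is invalid or insensitive to training. It is a valid description of reach, and it would move if training changed the attendee mix.
- That the whole evaluation is undermined. The primary outcomes and the Aim are unaffected.
- That adding subgroup analyses would settle the question. At about ±10.6 points for a 40% share, and ±0.70 to 0.88 kg for the interaction, they probably would not establish an effect on inequalities.

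The correction should be made, chiefly because it prevents an unsupported conclusion.

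**What to change.** 1. **Relabel (essential).** In sections 2.3(f) and 3.10.5, call the population comparison a description of reach and remove the inference about impact. State that the inequality part of section 2.1 is addressed only by exploratory analyses.

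2. **Use the data already requested.** In section 3.10.5, add an exploratory comparison of the 2023-to-2024 change in IMD distribution for trained versus untrained weight-service staff, with 2023 programmes grouped by the same staff. Do not read 2024 against 2023 alone as a training effect, because section 3.9.3 says management improved the service between those years. Report the pulmonary rehabilitation 2024 versus 2023 comparison as descriptive only, because it has no control. State the low precision.

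3. **Optional.** Add an exploratory training-by-IMD term to the weight regression in section 3.10.4 using the individual IMD from section 3.5, reported with a confidence interval. It covers consenters only (50% response assumed in section 3.9.2).

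Clustering by staff would widen the intervals in item 2. It is a separate issue for the plan as a whole.

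Cost: item 1 is wording. Item 2 needs one added analysis and a clear instruction on grouping the 2023 programmes. Item 3 needs one extra model term. None needs more participants or measurements.

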#### **4. Ethics**

Important ethical considerations for this mixed methods study include:

***Informed Consent***- Informed consent will be gained from all participants prior to their involvement [or their individual data being used]. This will ensure they have a clear understanding of what the research project is and what it is hoping to achieve through their involvement. Gaining informed consent will ensure participants understand and are happy with their role in the research. It will also make sure they understand what will be done with the data that will be collected from them.

Participant information sheets will be made available to all interested participants. They will have ample opportunity to read this and talk through any queries with the Lead Researcher prior to agreeing to participate. They will then sign a consent form immediately prior to being observed/recorded/completing outcome measure questionnaires/giving access to their clinical details /being interviewed. There will be separate consent forms for the different data collection methods. Participants will be informed that their participation is voluntary and that they can withdraw at any time if they wish.

***Low Literacy/English as a second language***- It is likely that some of the service-users invited to participate in the study will have low literacy skills or English as a second language. In order to address this, study materials will be written in plain English and designed in conjunction with the Health Literacy Officer and the project partnership group. A project information video will also be made available. When taking consent the Lead Researcher will go through each point with participants individually and summarise in plain language.

***Coercion and Inconvenience*** – Recruitment to research projects is difficult especially when recruiting busy healthcare/public health workers working in time

pressured and target driven environments. Participants will not be made to feel under any pressure to participate and their participation should be voluntary.

**Maintaining confidentiality**- This study will involve collecting a range of staff and patient data including clinical data. Confidentiality will therefore be extremely important and will be maintained throughout the study. All data collected will be anonymised/pseudonymised. The relevant information governance and information security procedures will be followed pertaining to the specific types of data that will be accessed and or generated.

## **5. Data management**

A data management plan will be completed to ensure the appropriate information governance practices are followed according to NHS, local government and University policies. Confidentiality and data sharing agreements will be put in place where appropriate, to ensure data from the NHS and local authority services is shared safely and securely between them and the University research team.

## **6.Timescales**

(Ethics outcome dependent)-

June- July 2024 - Recruitment of staff participants and pre intervention staff observations.

July- August 2024 - Delivery of training package and pre and immediately post intervention staff questionnaires.

July – November 2024 – Recruitment of service users and baseline outcome measures and Health Literacy Questionnaire data collection.

August– February 2025 – Service user post intervention outcome measures and Health Literacy Questionnaire data collection.

September – October 2024 – Two month follow up staff questionnaires.

October – November 2024 – Post intervention staff observations and/or recording of consultations.

November - January 2025 – Staff focus group interviews.

August 2024– March 2025 - Data analysis.

January – March 2025 – Write report/disseminate.

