#### 1.3.6 The services where the intervention will be used

The intervention will be used in two very different services.

1. Live Life Better Derbyshire tier 2 weight management services (Public Health, Derbyshire County Council). The aim of the programme is to help people lose weight. The service provides online and face to face group education and advice programmes that run for one session a week over a rolling 12 week period. The programmes have an accompanying website and resources. The

programme is available for all people in Derbyshire. Eight Public Health Improvement Advisors (HIA's) offer advice to groups of up to 25 people who need to lose weight. 33 programmes run across Derbyshire, 19 online and 14 face to face. Attenders are followed up at 12, 26 and 52 weeks and a weight maintenance programme is available.

2. Derbyshire Community Health Service Pulmonary Rehabilitation programme provided within the NHS. The aim of the programme is to improve people's exercise tolerance and respiratory health. This service provides a six week rolling face to face programme that runs across 6 venues in Derbyshire. 15 members of staff, a mixture of physiotherapists, healthcare assistants and specialist nurses, offer supervised exercise and education and advice to people who are limited by their respiratory condition in Derbyshire. The physiotherapists and specialist nurses lead the sessions and have most contact with patients. Up to 12 people attend two sessions a week over the six week period which are a combination of exercise and education.

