#### Secondary outcomes

- LLBD Weight Management Programme: The short form Warwick and Edinburgh Mental Health and Wellbeing Scale
- Pulmonary Rehabilitation Programme: Incremental shuttle walking test (in meters), Lung Information Needs Questionnaire (LINQ), Generalised Anxiety Disorder Assessment (GAD -7), Patient Health Questionnaire 9 (PHQ-9) and strength tests.

The weight management programme collects service users' weight at 0, 12 and 26 weeks. They collect the short form Warwick and Edinburgh Mental Health and Wellbeing Scale at 0 and 12 weeks.

The pulmonary rehabilitation service collects all measures at 0 and 6 weeks.

We will collect data at baseline and at the end of the programme for both services.

That is:

- 0, 12 and 26 weeks (weight only) for the weight management programme.
- 0 and 6 weeks for the pulmonary rehabilitation programme.

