### **3.6. Assessment of service users' subjective Health Literacy skills and health activation**

Services users will be asked to complete an additional questionnaire as part of the research. This will be two domains of the validated Health Literacy Questionnaire (Osborne *et al*; 2013). This is to understand whether their subjective Health Literacy and health activation skills have changed after attending the programmes by Verbal Health Literacy trained or non-trained staff.

The questionnaires will be completed at the same time as the routinely collected service data, that is the secondary outcomes for each service, at baseline, 6 weeks (pulmonary rehabilitation service) and 12 weeks (weight management service).

Service users will complete the questionnaire either electronically or in paper form as per the services current data collection practice. Or they will be posted to participants for them to complete and return. The mode of delivery will depend on the service's preference in order to minimise any extra burden on service staff during the research period.

Consent will be gained from all service user participants prior to collecting their data.

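### Section 6 has no step for collecting the 26-week weight of later entrants: the last recruit has at most 90 days of outcome collection against the 182 needed

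*Combined protocol and SAP*

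**What the plan says.** Section 3.5 makes weight in kilograms the primary outcome of the weight management programme. Under its secondary outcomes it sets the collection times: "0, 12 and 26 weeks (weight only) for the weight management programme". Section 3.9.2 expects weight, wellbeing and Health Literacy scores at three time points for about 330 users. It also expects a larger change in the trained group at both 12 and 26 weeks. Section 3.10.4 plans to describe mean weight loss at the three time points, then to compare the groups by regression on the change from baseline to 12 weeks.

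Section 6, marked as dependent on the ethics outcome, assigns July to November 2024 to "Recruitment of service users and baseline outcome measures and Health Literacy Questionnaire data collection". The follow-up line reads "August– February 2025 – Service user post intervention outcome measures and Health Literacy Questionnaire data collection". The closing lines are "August 2024– March 2025 - Data analysis" and "January – March 2025 – Write report/disseminate". Nothing in Section 6 is dated after March 2025.

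The recruitment period is given three ways: six months as likely in Section 3.8, a three-month study period in Section 3.9.2, and five calendar months in Section 6.

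**The concern.** Follow-up of 26 weeks needs half a year after the last enrolment, and Section 6 leaves about three months. No section schedules a later extract or restricts the 26-week measure to early entrants.

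The theory of change in Section 1.3.7 includes maintaining weight loss, and Section 3.9.3 notes that people can regain weight after an initial loss. Week 26 is the only planned individual measure after the 12-week programme ends. If the timetable stands, the 26-week mean loss would come from a smaller, earlier set of people than the 12-week mean loss. An apparent trend between the two could then reflect who is included and not what happened to weight. The expected larger 26-week change in the trained group would rest on early entrants only.

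**Working it through.** **The plan's own figure.** Section 3.9.2 has 33 programmes of 15 to 25 people: 33 × 15 = 495 and 33 × 25 = 825, with midpoint (495 + 825) / 2 = 660. At a 50% response, 660 × 0.50 = 330. The stated number reproduces. It contains no allowance for users who cannot reach week 26 in time.

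**Inputs.** Enrolment July to November 2024, read as 1 July to 30 November, 153 days (Section 6). Collection to February 2025, read as 28 February, the latest possible reading (Section 6). Follow-up of 26 weeks = 182 days (Section 3.5). Even entry over the window is an assumption; the documents say only that entry is rolling.

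**Time available to the last entrant.** 30 November 2024 to 28 February 2025 = 90 days. Shortfall: 182 − 90 = 92 days. Week 26 for this person: 30 November 2024 + 182 days = 31 May 2025.

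**Latest entry that reaches week 26.** 28 February 2025 − 182 days = 30 August 2024. From 1 July to 30 August is 61 entry days.

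**Share missing week 26** = 1 − (qualifying entry days / all entry days):

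| Entry window (2024) | End of collection | Qualifying / all days | Share missing |
|---|---|---|---|
| July-November | 28 Feb 2025 | 61 / 153 | 60.1% |
| July-September | 28 Feb 2025 | 61 / 92 | 33.7% |
| July-December | 28 Feb 2025 | 61 / 184 | 66.8% |
| August-November | 28 Feb 2025 | 30 / 122 | 75.4% |
| September-November | 28 Feb 2025 | 0 / 91 | 100% |
| July-November | 31 Mar 2025 | 92 / 153 | 39.9% |

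The last row lets collection run until analysis closes; the cut-off is then 31 March 2025 − 182 days = 30 September 2024. The August and September starts are included because Section 3.8 enrols users after staff have, or have not, been trained, and Section 6 delivers the training in July and August.

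**Week 12.** 30 November 2024 + 84 days = 22 February 2025, six days inside the window. All July-November entrants can reach week 12.

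These shares are timing only, before any attrition.

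**The case against.** The strongest reply is that little hangs on the 26-week result. The only between-group regression on individual data is at 12 weeks, and the sample size calculation in Section 3.9.3 is also for 12 weeks. The service records the weight anyway: "Attenders are followed up at 12, 26 and 52 weeks and a weight maintenance programme is available". The data need not be lost, and Section 6 is provisional. All of this stands, and it limits the consequence. It does not close the gap: no step obtains or analyses those weights after March 2025, and if all dates move together the 92-day shortfall is unchanged. If the February line was meant only for end-of-programme measures, Section 6 has no slot for week 26 at all.

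A reader might infer more than the documents support:

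- *That 60% is a firm figure, or that a known number of the 330 is lost.* The share depends on even entry from 1 July. The 330 is tied to a three-month period, not to Section 6's five months, and no 26-week completion rate is given. A head count would be spurious.
- *That the main comparison or its power fails.* On Section 6's dates week 12 fits. The 252 per group in Section 3.9.3 is a service-level calculation and is not presented as the sample size of the individual-level regression. Week 12 would be missed only if recruitment ran into December with collection still ending in February, a combination that no section states.
- *That trained and untrained groups lose different people.* Section 3.2 has comparison users join over the same period, so differential loss is not established.
- *That each person's 26-week loss is distorted.* Loss is measured from a person's own baseline; the problem is that the 12- and 26-week means cover different sets of people.
- *That the aggregate 26-week means in Section 3.7 fail too.* They may be affected, but the documents give no dates from which to judge.

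**Conclusion.** The point holds as an inconsistency between the timetable and the stated follow-up of a primary outcome. The certain part is the date arithmetic: on the most generous reading of the closing month, the last entrant is 92 days short, and nobody enrolled after 30 August 2024 reaches week 26 by the end of February 2025. The share affected rests on an assumed even entry: about 60% on Section 6's own window, from 34% to 100% over the other plausible windows, and still 40% if collection ran to the end of March. Weight at three time points for about 330 users is therefore not deliverable as scheduled. The damage is confined to the descriptive 26-week result and the expectation attached to it. The plan should be corrected, but its 12-week analysis is not put in doubt by this gap.

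**What to change.** First reconcile the recruitment period across Sections 3.8 (six months), 3.9.2 (three) and 6 (five). Then choose one of two routes.

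**(a) Preferred.** Add to Section 6 a later extract of the routinely recorded 26-week weights, at least 26 weeks after the last enrolment (31 May 2025 on current dates), and report the 12-week results on the current timetable. The cost is one further extract, and extending analysis, reporting and any data-sharing arrangements past March 2025. This works whatever the entry window.

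**(b) Otherwise.** Limit 26-week reporting to users enrolled early enough to reach it. Give the number, show the 12- and 26-week mean weight losses in that same subset, label the result descriptive, and restate in Section 3.9.2 the number expected at 26 weeks. The edit is wording only, but the 30 August cut-off falls inside the July-August training window, so the subset may be very small or empty. If it is empty, the individual 26-week outcome should be withdrawn.

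Separately, correct Sections 3.9.2 and 3.10.4 so that the third time point applies to weight only. On wellbeing, Section 3.5 says of the service: "They collect the short form Warwick and Edinburgh Mental Health and Wellbeing Scale at 0 and 12 weeks". Section 3.6 likewise places the Health Literacy questionnaire at baseline and 12 weeks for this service. This is a drafting correction with no cost.
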